#### Section 3: Prior Therapy

#### 4) Which of the following insulin pumps did you use previously?

- (If you have used several, check the one that you used 'most recently' prior to Hybrid Closed Loop System clinical study)
- Never used an insulin pump
- MiniMede 670G system (Medtronic)
- MiniMed® 530G System (Medtronic)
- □ MiniMed® Paradigm Revel™ 523/723 System (Medtronic)
- MiniMed® 640G System (Medtronic)
- □ MiniMed® Veo™ System (Medtronic)
- Tandem Basal-IQ
- Tandem t:slim®
- Tandem t:flex®
- ACCU-CHEK® Spirit (Roche)
- ACCU-CHEK® Spirit Combo (Roche)
- Animas® Vibe® System (Animas)
- □ OneTouch® Ping™ (Animas)
- OmniPod® (Insulet)
- Other (Please specify\_
- Can't recall specific pump/brand/model

 How satisfied were you with your previous insulin pump system, prior to using the Advanced Hybrid Closed Loop System?

Extremely	Very	Satisfied	Somewhat	Not	Not Sure
satisfied	satisfied		satisfied	satisfied	
5	4	3	2	1	0
0	0	0	0	0	0

- 6) Prior to the Advanced Hybrid Closed Loop clinical trial, had you previously used Continuous Glucose Monitoring (CGM)?
  - Yes
  - 🗆 No
  - Not sure
- - a) Which CGM device did you use previously (prior to using Advanced Hybrid Closed Loop system)? (Skip if never used CGM before)
    - Medtronic Enlite® Glucose Sensor
    - Medtronic Guardian Sensor 3 Sensor
    - Abbott FreeStyle® Libre (Abbott)
    - Dexcom G4 Platinum
    - Dexcom G5 Mobile CGM System
    - Dexcom G6 Mobile CGM System
    - Other CGM product (Please specify: \_\_\_\_\_)
    - I can't recall

- b) Prior to the Advanced Hybrid Closed Loop system, how frequently did you wear the CGM sensor? (Skip if never used CGM before)
  - Every day
  - Nearly every day
  - A few weeks per month
  - About one week per month
  - About 2-4 times a year
  - Less than once a year
  - I don't recall

#### 8) How satisfied were you with your previous CGM, prior to using the Advanced Hybrid Closed Loop System?

Extremely satisfied	Very satisfied	Satisfied	Somewhat satisfied	Not satisfied	Not Sure
5	4	3	2	1	0
0	0	0	0	0	0

#### 9) How would you rate your ability to manage the following on your previous system?

		Excellent	Very Good	Good	Fair	Poor	No Opinion
		5	4	3	2	1	0
1	Reducing lows at night	0	0	0	0	0	0
2	Reducing lows during the day	0	0	0	0	0	0
3	Reducing highs after meals	0	0	0	0	0	0
4	Reduce the effort to carb count	0	0	0	0	0	0
5	Reduce the effort to bolus for my meals	0	0	0	0	0	0
6	Reducing day-to-day effort managing diabetes	0	0	0	0	0	0
7	Reducing mental effort managing diabetes (how much one needs to think about it)	o	0	0	0	0	0
8	Improving blood glucose (blood sugar) time-in-range	0	0	0	0	0	0
9	Ease of use of the system	0	0	0	0	0	0
10	Ease of learning how to use the system	0	0	0	0	0	0

#### Section 4: Advanced Hybrid Closed Loop system Expectations

- 10) Once you start using the Advanced Hybrid Closed Loop system, in which of the following areas are you expecting to see improvement? Please rank your top 10 improvements from 1 being the feature that you would like to see the most improvement, 2 being second most improvement, etc.
  - Less day-to-day effort managing my diabetes
  - Better A1C
  - Not having to fingerstick
  - Fewer lows
  - Less amount of time to come down from a high
  - Less effort to come down from a high
  - Not having to carb count
  - More time in range
  - No need to bolus for meals
  - No need to correct my high glucose values
  - Ability to control my pump using my phone
  - Other: \_\_\_\_\_\_

#### Section 5: Profiling, & Demographics

- 11) Approximately what range was most recent HBA1c result?
  - □ [12] 5.0 or lower
  - [11] 5.1 to 5.5
  - □ [10] 5.6 to 6.0
  - [9] 6.1 to 6.5
  - □ [8] 6.6 to 7.0
  - [7] 7.1 to 7.5
  - [6] 7.6 to 8.0
  - □ [5] 8.1 to 8.5
  - [4] 8.6 to 9.0
  - [3] 9.1 to 9.5
  - [2] 9.6 to 10.0
  - [1] Greater than 10.0
  - [0] Not sure

#### 12) How satisfied are you with your current HbA1C results?

- □ [5] Extremely Satisfied
- [4] Very Satisfied
- [3] Somewhat Satisfied
- [2] Not Very Satisfied
- [1] Not at all Satisfied
- [0] Not sure

13) How many times do you test your blood glucose in a single day? \_\_\_\_\_ [RANGE: 1-20]

- 14) Is your carbohydrate intake tracked on a regular basis?
  - □ [2] Yes, very regularly
  - □ [1] Yes, although not necessarily regularly
  - [0] No
  - a) In your opinion, how well are you able to calculate your carbohydrate intake?
    - [5] Extremely Well
    - [4] Very Well
    - [3] Somewhat Well
    - [2] Not Very Well
    - [1] Not at all Well
    - [0] I do not count carbohydrates
  - b) In your opinion, how challenging is it to calculate your carbohydrate intake?
    - [4] Very challenging
    - [3] Somewhat challenging
    - [2] Not challenging
    - [1] Not at all challenging
    - [0] Not sure

- 15) On average how would you describe your meal bolus behavior?
  - [3] I only bolus for meals if it is convenient to do so
  - □ [2] I usually bolus after meals
  - □ [1] I usually bolus during meals
  - [0] I usually bolus before meals

16) What is your birth YEAR?

- 17) What is your gender?
  - Female
  - Male
- 18) Have you participated in prior diabetes clinical trials?
  - Yes
  - □ No
  - a) When did you last participate in a diabetes clinical trial? (Skip this question if never participated in a clinical study)
    - [3] Within the past 6 months
    - [2] About 7-12 months ago
    - [1] About 1-2 years ago
    - [0] Greater than 3 years ago

# MARKET RESEARCH SURVEY

# Medtronic

# Advanced Hybrid Closed Loop System Post Study Patient Questionnaire

Patient ID: Study ID: Date: Verified by (Site Employee):

Thank you for taking the time to complete this questionnaire. Your answers are valuable to us. Your answers are confidential. There is no right or wrong answers. Please take your time when answering the questions. The questionnaire should take about 20 minutes to complete.

Note: throughout this survey, we are referring to your current study device Medtronic MiniMed insulin pump and sensor as the "Advanced Hybrid Closed Loop" or "AHCL" system. Approval/Respondent Qualification

[Age] Are you 18 years of age or older?

- I Yes
- D No

If you are under 18 years of age, do you have the permission of your parent or guardian to complete this survey?

No (You must have permission in order to continue)

Are you the individual who participated in the Advanced Hybrid Closed Loop Clinical Study, or a care partner?

- I am the actual participant
- □ I am a care partner of an individual under the age of 18 (who is participating in the study)
- □ I am a care partner of another adult (who is participating in the study)

If a caregiver, from this point forward, please answer the questions on behalf of the individual who will actually be using the Advanced Hybrid Closed Loop system. 1. Considering your experience with the overall AHCL System, how likely are you to recommend it to others?

2. How would you rate the AHCL System for the following categories? Please indicate below.

		1 Not Sure	2 Poor	3 Fair	4 Good	5 Very Good	6 Excellent
1.	Overall rating of the Pump	0	0	0	0	0	0
2.	Overall rating of the sensor	0	0	0	0	0	0
3.	Overall control of low blood glucose	0	0	0	0	0	0
4.	Overall nighttime control of blood glucose	0	0	0	0	0	0
5.	Maximizing time spent in control	0	0	0	0	0	0
6.	Overall control of glucose levels	0	0	0	0	0	0
7.	Reducing lows caused by physical activities	0	0	0	0	0	0
8.	Overall control of blood glucose levels after a meal	0	0	0	0	0	0
9.	Overall control of high glucose levels after not bolusing for meals	0	0	0	0	0	0
10.	Overall control of high blood glucose	0	0	0	0	0	0
11.	Overall ease of use of the system	0	0	0	0	0	0
12.	Ease of use of the pump	0	0	0	0	0	0
13.	Ease of use of the sensor	0	0	0	0	0	0
14.	Overall helpfulness of the alarms	0	0	0	0	0	0

#### Please compare the AHCL system to your previous therapy system.

 Considering everything about the AHCL system, which of the following phrases best describes how you feel about it?

> The best therapy system I have ever used or tried Slightly better than any other therapy system I have ever used or tried About the same as any other therapy system I have ever used or tried

Slightly worse than any other therapy system I have ever used or tried

The worst therapy system I have ever used or tried

4. Considering everything about the AHCL system, which of the following phrases best describes how you feel about it in comparison with your previous therapy system?

Much better than my previous therapy system Somewhat better than my previous therapy system About the same as my previous therapy system Somewhat worse than my previous therapy system Much worse than my previous therapy system

This document is electronically controlled

Medtronic Confidential

Document Template MP9198035-026DOC\_E

5. Comparing the AHCL system to your previous therapy system, which would you prefer for the following characteristics?

		1 Prefer AHCL SYSTEM	2 Prefer Previous Therapy System	3 Prefer Both Equally	4 Prefer Neither
1.	Overall performance	0	0	0	0
2.	Overall control of blood glucose levels	0	0	0	0
З.	Maximize time spent in control	0	0	0	0
4.	Control of low blood glucose	0	0	0	0
5.	Control of high blood glucose	0	0	0	0
6.	Ease of use	0	0	0	0
7.	Ease of adjusting insulin therapy	0	0	0	0
8.	Helping to meet my glucose targets (therapy goals?)	0	0	0	0
9.	Effort spent managing my diabetes	0	0	0	0
10	Time spent thinking or worrying about my diabetes	0	0	0	0
11	Freedom with my food choices	0	0	0	0
12	Effort around mealtime	0	0	0	0
13	Effort of carb counting	0	0	0	0

#### 6. Please indicate how much you AGREE or DISAGREE with each of the following statements about the overall AHCL system?

		1	2	3	4	5
		Strongly	Slightly	Neither Agree	Slightly	Strongly
		Disagree	Disagree	Nor Disagree	Agree	Agree
1.	Gives me peace of mind	0	0	0	0	0
2.	Helps me engage in my favorite hobbies	0	0	0	0	0
З.	Helps my overall physical well being	0	0	0	0	0
4.	Gives me confidence in my diabetes management	0	0	0	0	0
5.	let's me achieve better control with less effort	0	0	0	0	0
6.	Lets me put in less effort in checking blood glucose levels and calibrating sensors	0	0	0	0	0
7.	Lets me put in less effort in carb counting	0	0	0	0	0
8.	Lets me put in less effort in treating highs	0	0	0	0	0
9.	Helps me lower my A1C	0	0	0	0	0
10.	Helps me and my family worry less	0	0	0	0	0

This document is electronically controlled Medtronic Confidential Document Template MP9198035-026DOC\_E

		1 Strongly Disagree	2 Slightly Disagree	3 Neither Agree Nor Disagree	4 Slightly Agree	5 Strongly Agree
11.	Makes me feel more rested in the morning and with more energy for the whole day	0	0	0	0	0
12.	It helps me feel calm and relaxed	0	0	0	0	0
13.	Improves overall quality of life	0	0	0	0	0
14.	Helps me spend more time in range (time between 3.9mmol/L and 10mmol/L)	0	0	0	0	0
15.	Helps make meal time easier	0	0	0	0	0
16.	I worry less about what I eat	0	0	0	0	0
17.	Helps me think less about my diabetes in social setting	0	0	0	0	0
18.	Helps me sleep better at night	0	0	0	0	0
19.	Lets me put in less effort in managing my diabetes	0	0	0	0	0
20.	Helps make mealtime less stressful	0	0	0	0	0
21.	Helps me feel less restricted around meals	0	0	0	0	0
22.	Gives me freedom with my food choices	0	0	0	0	0
23.	I trust the SmartGuard (Auto Mode) technology	0	0	0	0	0

7. Please indicate how much you AGREE or DISAGREE with the following statements regarding your experience with the AHCL system.

		1 Strongly Disagree	2 Slightly Disagree	3 Neither Agree Nor Disagree	4 Slightly Agree	5 Strongly Agree
1.	I think that I would like to use this system frequently	0	0	0	0	0
2.	I found the system unnecessarily complex	0	0	0	0	0
3.	I thought the system was easy to use	0	0	0	0	0
4.	I think that I would need the support of a technical person to be able to use this system	0	0	0	0	0
5.	I found the various functions in this system were well integrated	0	0	0	0	0
6.	I thought there was too much inconsistency in this system	0	0	0	0	0
7.	I would imagine that most people would learn to use this system very quickly	0	0	0	0	0
8.	I found the system very cumbersome to use	0	0	0	0	0
9.	I felt very confident using the system	0	0	0	0	0
10.	I needed to learn a lot of things before I could get going with this system	0	0	0	0	0
11.	The amount of time spent learning to use the system was reasonable	0	0	0	0	0

 
6.
 
7.
 
8.
 
9.
 
10.
 
11.
 
	were well integrated I thought there was too much inconsistency in this system I would imagine that most people would learn to use this system very quickly I found the system very cumbersome to use I felt very confident using the system I needed to learn a lot of things before I could get going with this system The amount of time spent learning to use the system was reasonable	0 0 0 0 0	0 0 0 0 0	0 0 0 0 0 0	0 0 0 0 0 0	

This document is electronically controlled Medtronic Confidential Document Template MP9198035-026DOC\_E

8. Please indicate how much you AGREE or DISAGREE with the following statements regarding your experience with not having bolusing for meal while using the AHCL system.

		1 Strongly Disagree	2 Slightly Disagree	3 Neither Agree Nor Disagree	4 Slightly Agree	5 Strongly Agree
1.	The system helps me avoid highs if I forget to dose for a meal	0	0	0	0	0
2.	The system protects me if I forget to dose for a meal	0	0	0	0	0
3.	I feel like I can skip bolusing for snacks and the system still takes care of my diabetes	0	0	0	0	0
4.	I feel like I can skip bolusing for light meals (<40g carb) and the system still takes care of my diabetes	0	0	0	0	0
5.	I feel like I can skip bolusing for all meals and the system still takes care of my diabetes	0	0	0	0	0

# End of Survey – Thank you for your participation!

This document is electronically controlled Medtronic Confidential Document Template MP9198035-026DOC\_E

# 16.11 Biomarker Collection Methodology

Assays required:

Assay	Sample type	Sample size (singliplicate)	Duplicates analysed?	Comments
CAMs				
sVCAM	EDTA plasma OR serum	20ul	YES	dead volume 100ul
sICAM	EDTA plasma OR serum	20ul	YES	dead volume 100ul
s-eSelectin	EDTA plasma OR serum	30ul	YES	dead volume 100ul
oxLDL	EDTA plasma OR serum	25ul	YES	dead volume 100ul
МРО	EDTA plasma OR serum	25ul	YES	dead volume 100ul
microRNA	EDTA plasma	200ul	NO	
Telomerase				TBA as assessing various assays
DNA methylation	whole blood (EDTA)	1mL	NO	
Glycomark	EDTA plasma OR serum	4ul	NO	dead volume 200ul
Isoprostanes	EDTA plasma OR serum	250ul	NO	
Proteomics	EDTA plasma	50ul	NO	CTC via Aust. Proteomics Facility
Clotting profile	GC/MS EDTA plasma,	400 ul		At CTC ([name])

Collection tubes are assumed to be BD plastic vacutainers with draw volume of 4mL.

The biomarker samples below are to be collected at V3 and V6. K2EDTA BD catalog number: 367839 (lavender) Serum BD catalog number: 367954 (gold) SST (serum separator tube)

Sample type	Analysis	Tubes for analysis	Biobanking	Tubes for biobanking
Serum			4 mL	1 x 4 mL
EDTA blood	8 mL	2 x 4mL	8 mL	2 x 4 mL
Urine			50 mL	container

Biomarker samples processing:

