Vascular complications are a major cause of morbidity and premature mortality in people with diabetes, due to traditional (adiposity, dyslipidaemia, hypertension, smoking, poor glycaemic control) and novel vascular disease risk factors (subtle changes in lipoproteins, such as oxidation and nonenzymatic glycation, Advanced Glycation End Products (AGEs), oxidative stress, inflammation, altered angiogenesis, prothrombotic tendencies, glycaemic variability, impaired vasoregulation, and more recently recognised molecular changes like telomere length, activity of telomerase (the enzyme which controls telomere length), microRNAs and DNA methylation. Collection of suitable samples and their analyses are particularly relevant to this study as vascular damage starts early in life, particularly in individuals with poor glycaemic control. Improved metabolic control may at least partially reduce adverse risk factor profiles. Furthermore, we have cross-sectional data demonstrating improved vascular function and a less adverse novel vascular risk profile in insulin pump treated T1D patients and evidence that molecular markers can be improved by existent and emerging drug therapies.

2.2 Name and description of the intervention or product(s) used in this trial, including investigational product(s) and comparator product/s (if applicable). Include status of product registration (i.e. registration on Australian Therapeutic Goods Registry, or equivalent).

The **Medtronic advanced hybrid closed loop system** is an investigational device which compromises an advanced closed loop algorithm with the compatible, glucose sensor and glucose sensor transmitter.

The algorithm uses a modified proportional integrative derivative (PID) model, with insulin feedback and additional safety features. The algorithm receives glucose data every 5 minutes from the sensor, and a "basal rate" insulin delivery is computed and adjusted every five minutes. Therefore, standard "basal" insulin that is pre-programmed in regular insulin pump therapy is replaced by the algorithmderived insulin delivery (given as a micro-bolus every 5 minutes). Meals will still be announced, and an insulin bolus delivered according to the individualised patient's carbohydrate ratio.

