#### Aims

The primary aim of the study is

1) To determine the effect of hybrid closed loop on the change in glycated haemoglobin (HbA1c) in adolescents with suboptimal glycaemic control (HbA1c>8.5%) and comparing this technology with standard care.

The secondary aims of the study are

- 2) To determine the effect of hybrid closed loop on percentage time in range compared to standard therapy
- 3) To determine the effect of hybrid closed loop on *psychological and social well-being* compared to standard care
- 4) To determine the effect of hybrid closed loop on glycaemic parameters on hypoglycaemia and hyperglycaemia compared to standard therapy
- 5) To determine the effect of hybrid closed loop technology on *retinopathy*
- 6) To determine the effect of hybrid closed loop technology on the metabolic biomarkers
- 7) To determine the cost effectiveness of hybrid closed loop technology compared to standard therapy in long term.
- 8) To determine the technology-user" interactions ("human factors") to improve translational strategies

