#### VISIT 3 (4-6 hours)

This visit is the randomisation visit, and allocation is dependent on the stratifications detailed in Section 4.3.

The following data will be collected prior to randomisation:

- 1. Diabetes clinical
  - a. HbA1c
  - b. Total daily dose of insulin (mean of previous 7 days)
  - c. Severe hypoglycaemia in the run-in period
  - d. Diabetic ketoacidosis in the run-in period
  - e. Admissions in the run-in period
  - f. Pump upload
  - g. Sensor data in the 2 weeks prior to the study (in participants on CGM)
- 2. Diabetes education/review
  - a. Diabetes education: Diabetes educator session (2 to 4 hrs) as refresher to re-educate and optimise standard diabetes management
  - b. Carbohydrate Counting: Dietician review (1 to 2 hours)
     The duration of the session is variable according to the prior knowledge of the participant.
- 3. Retinal photographs, will be collected and retained for centralised assessment
- 4. INSPIRE questionnaire (baseline for participants randomised to AHCL)
- 5. Medtronic AHCL System Background Patient Questionnaire (optional)

6. Biomarkers

A detailed description of sample preparation for biomarkers is found in appendix

- 12mL of blood and 50mL of urine will be collected in fasting state
- a. Cell Adhesion Molecules (CAM)S
- b. Soluble vascular cell adhesion molecules sVCAM
- c. Soluble intercellular adhesion molecules sICAM
- d. s-e Selectin
- e. Oxidized Low density lipoprotein
- f. Myeloperoxidase.
- g. MicroRNA signatures for arterial, renal and retinal complications
- h. Telomerase
- i. DNA methylation/acetylation
- j. Glycomark
- k. Isoprostanes and proteomics
- I. Clotting profile

VISIT 4 (participants randomised to AHCL arm)

CSII to AHCL: Participant 780G, CGM education and AHCL training.

Visit 4A: Pump training (2 hours)

Participants will be trained on how to use the Medtronic 780G insulin pump. Participants will be provided with Roche Accu-Chek®glucometer along with the glucose strips for the study.

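### The clotting profile is undefined and assigned to EDTA plasma with no citrate tube listed, so any clot-based test in it could not be measured validly

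*Protocol*

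**What the plan says.** Section 4.2 lists "Clotting profile" as the last biomarker entry at Visit 3, and the Visit 8 list repeats it. Neither list, nor any other part of the protocol, names the component tests. For the sample, the Visit 3 text says "12mL of blood and 50mL of urine will be collected in fasting state", and Visit 8 gives the same volumes.

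Appendix 16.11 sets out the handling. In its assay table the specimen cell for the clotting profile reads "GC/MS EDTA plasma", with 400 ul as the sample size. On tubes it says "Collection tubes are assumed to be BD plastic vacutainers with draw volume of 4mL", and it identifies two types: "K2EDTA BD catalog number: 367839 (lavender) Serum BD catalog number: 367954 (gold) SST (serum separator tube". The tube table below has three rows only: serum (one 4 mL tube, biobanking), EDTA blood (two 4 mL tubes for analysis and two for biobanking) and urine (50 mL, biobanking).

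The related aim in Section 3.1 is "To determine the effect of hybrid closed loop technology on the metabolic biomarkers". The rationale in Section 2 mentions "prothrombotic tendencies" within a list of novel vascular risk factors.

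**The concern.** In ordinary laboratory usage a clotting profile is a set of clot-based tests. EDTA prevents clotting by binding the calcium that those tests depend on, and serum has already clotted, so its fibrinogen and several factors have been consumed. Clot-based tests normally use citrate plasma, and no citrate tube is listed.

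A wrong tube cannot be corrected at the analysis stage. The Visit 3 sample is taken before randomisation, and once treatment starts there is no second chance at baseline. The biobank holds the same two blood specimen types, so it offers no fallback. If the panel has a clot-based part, that part would be missing or artefactual in both arms at both visits, and no between-arm comparison of it could be made.

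**Working it through.** No statistical figure in the protocol bears on this point. The check sets the specimen required against the specimens collected.

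**1. Specimen against tube**

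| Place | What it gives |
|---|---|
| 4.2, Visits 3 and 8 | Clotting profile planned, components not stated |
| 16.11, assay table | EDTA plasma, 400 ul |
| 16.11, tube catalogue line | K2EDTA and serum separator only |
| 16.11, tube table | Serum, EDTA blood, urine |
| Anywhere in the protocol | No citrate tube or citrate plasma |

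The catalogue line and the tube table agree with each other, and neither depends on the clotting row of the assay table.

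**2. Is volume the limit?** Plasma or serum needed per visit, using 2 x sample + dead volume for the assays run in duplicate:

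- sVCAM 2 x 20 + 100 = 140 ul
- sICAM 2 x 20 + 100 = 140 ul
- s-eSelectin 2 x 30 + 100 = 160 ul
- oxLDL 2 x 25 + 100 = 150 ul
- MPO 2 x 25 + 100 = 150 ul
- microRNA 200 ul
- Glycomark 4 + 200 = 204 ul
- Isoprostanes 250 ul
- Proteomics 50 ul
- Clotting profile 400 ul

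The sum is 1,844 ul. Telomerase is left out because its assay is still to be decided. DNA methylation takes 1 mL of whole EDTA blood, which leaves 8 - 1 = 7 mL for plasma; 1.844 / 7 = 26%, so a plasma yield of just over a quarter of the blood volume is enough. Volume is not the constraint. The anticoagulant is.

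**3. How many collections are exposed?** With 50 participants (Section 9.2) and two visits, at most 50 x 2 = 100. If the full 15% dropout assumed in Section 9.2 occurred before the second collection, it would be 50 + 0.85 x 50 = 92.5, or about 92. These counts matter only for clot-based components.

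**4. Two conflicts that affect any correction**

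- Visits: 16.11 collects at V3 and V6. The Visit 8 description and the Section 4.8 schedule place the second collection at Visit 8. Section 4.2 puts Visit 6 at 23 weeks and Visit 8 at 26 weeks.
- Blood volume: the tubes in 16.11 total 4 (serum) + 8 (EDTA analysis) + 8 (EDTA biobanking) = 20 mL. Visits 3 and 8 state 12 mL. The EDTA analysis tubes plus the serum tube already make 8 + 4 = 12 mL. If 12 mL is the limit, there may be no EDTA biobanking tube to exchange.

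**The case against.** The strongest reply is that the protocol never calls the panel functional. No clotting time, clottable fibrinogen or factor activity is named, and haemostasis markers measured by antigen or mass can be run on EDTA plasma. The GC/MS entry, if it belongs to the clotting row, points to a method that is not clot-based. This stands, and it limits the finding to whatever clot-based components the panel contains.

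A second reply is that the evidence is damaged by text extraction. The clotting cell has a method name in the specimen column and ends on a comma, so a second specimen type may have dropped out. The heading on sample processing at the end of 16.11 has nothing beneath it. It is therefore fair to say that no citrate tube is shown, and not that none was ever intended. The tube catalogue line and the tube table read cleanly, however, and both omit citrate, so the point does not rest on the damaged cell.

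A reader might go further and infer that the prothrombotic part of the biomarker aim is lost, or that every planned clotting result is invalid. The document does not support this. Aim 6 speaks of metabolic biomarkers in general. Prothrombotic tendencies appear only as background in the rationale. Section 3.1 has no biomarker hypothesis, and the secondary endpoints in Section 4.1 do not include biomarkers. With the components undefined, it cannot be said that all, or even most, of the planned clotting results are clot-based.

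**Conclusion.** The concern holds in a limited form. As written, Appendix 16.11 cannot deliver a valid clot-based measurement at either biomarker visit, and the stored samples could not supply one later. Antigen-type markers validated in EDTA plasma remain measurable. The size is up to 100 collections (about 92 with the full assumed dropout) for one of twelve lettered biomarker entries. If the panel is wholly antigen-based, no results are lost and the defect is a misleading, undefined label.

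The conclusion rests on two assumptions: that the tube line and tube table are complete, and the general laboratory fact that EDTA plasma and serum do not support clot-based tests, which the protocol itself does not discuss. The primary endpoint, power and alpha are unaffected.

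**What to change.** State in Appendix 16.11 and in the Visit 3 and Visit 8 lists which tests make up the clotting profile, and match the tube to them.

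- If any component is clot-based, replace one of the two 4 mL EDTA biobanking tubes with a sodium-citrate tube of the same draw volume at both biomarker visits, and assign the clotting profile to citrate plasma. The 16.11 total stays at 4 + 8 + 4 + 4 = 20 mL.
- If the panel is antigen-based only, replace the label with the names of the EDTA-validated markers. No tube changes.

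In the same edit, reconcile the second collection visit (V6 in 16.11 against Visit 8 in Sections 4.2 and 4.8) and the blood volume (20 mL of tubes against 12 mL). The volume must be settled first, because the exchange assumes that an EDTA biobanking tube is actually drawn.

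The cost is an appendix edit and, under the first option, 4 mL less EDTA blood in the biobank per visit (4 mL instead of 8 mL). Neither option repairs samples already taken, so the change helps only collections still to come.
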